## **7.2 DATA ANALYSIS**

### **7.2.1 ORIGINAL PLANNED DATA ANALYSIS**

All statistical aspects of the trial will be governed by a comprehensive Statistical Analysis Plan (SAP), which will be authored by the trial statistician and approved by both the Trial Steering Committee (TSC) and Independent Data Monitoring Committee (iDMC). The final sample size will be determined by the pre-specified group sequential design, and there will be a single final analysis and reporting of the trial at that point. As a non-inferiority design, both an Intention to Treat (ITT) and a suitably specified Per Protocol analysis will be presented, with primacy given to the ITT approach (albeit it can be that for a non-inferiority design the Per Protocol approach is the more conservative under the null hypothesis). Missing data will be kept to a minimum by good design and conduct, including evidence based processes to maximise retention. It is expected that those missing primary outcomes will be <10% but nonetheless the robustness of the findings under the ITT approach will be assessed by adjusting for these missing data using Rubin's multiple imputation approach under an assumption of missing at random. The primary outcome (VTE at 90 days, Yes/No) will be analysed using a mixed effects logistic regression, with centre as a random effect, VTE risk (moderate vs high) and other to be pre-specified baseline factors as covariates. Secondary outcomes will be assessed in a similar fashion with generalised linear models appropriate to the distribution of the outcome. The level of statistical significance will be taken to be a nominal 0.05. We will undertake for the record the analysis of cohorts 1, 2 and 3 on those recruited prior to 20th December 2017 in line with the original data analysis plan v1.0. Under the new analysis, cohorts 1-4 will be analysed separately. The group sequential analysis is abandoned.

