### 6.1 BASELINE VISIT

Once consented, participants will undergo detailed clinical assessment by the research nurse as part of the baseline evaluation. Recorded assessments will include:

- Demographic details (age, sex, ethnicity)
- Pregnancy test for woman of child bearing age
- General clinical details (body mass index, comorbidities, medication history)

Additional assessments will include:

- EuroQuol 5D (EQ5D) generic quality of life assessment

At this point, eligible participants will be randomised 1:1 via the trial website to either:

- Current 'standard' combined low dose LMWH with GCS mechanical thromboprophylaxis, or
- Low dose LMWH pharmacoprophylaxis alone

The participant will be given further materials including:

- Participant VTE diary
- GCS compliance diary (GCS trial arm only)
- Participant contact and reminder card
- LMWH reminder card

And will proceed to their elective surgery as planned. Women of child bearing age will have another pregnancy test on the day of surgery if there is a possibility of pregnancy since the last test.

Post operatively the participant will be reviewed clinically as per standard care. This will include vigilance for the VTE.

## 6.2 FOLLOW-UP VISIT 1

The participant will be either seen in person at 1 week after surgery or at discharge (whichever is earlier). Recorded assessments will include:

- Any diagnosis of VTE (Anonymised copies of any duplexes will be forwarded to the Study Coordinating Centre at Imperial College London)
- Any symptoms or signs of VTE (if there is clinical suspicion identified by the research nurse which has not been identified by the clinical team, the research nurse will inform the clinical team who will proceed to imaging if appropriate).
- EuroQuol 5D (EQ5D) generic quality of life assessment
- Review of participant diary (completed until discharge)
- Collection of stocking compliance diary
- Collection of Adverse or Serious Adverse Events

If participant have been discharged without being assessed they will be contacted at either 1 week or as soon as possible.

## 6.3 FOLLOW-UP VISIT 2

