## 7. STATISTICS AND DATA ANALYSIS

### 7.1 SAMPLE SIZE

#### 7.1.1 ORIGINAL SAMPLE SIZE- APPLICABLE UP TO JANUARY 2018

With a one-sided test at 2.5% level of significance (equivalent to a 2-sided test at 5%) the trial has 90% power to conclude that the single pharmacological intervention is non-inferior to the combined intervention (pharmacology and stockings) assuming an event rate of 6% of VTE at 90 days in the combined group and a non-inferiority margin of 3.5%, and a conservative loss to follow up (i.e. non-evaluable for the primary outcome) rate of 10%. The maximum sample size required under this group sequential design, including allowance for loss to follow up, is a total of 2236.

We assume that the standard of care gives a VTE at 90 days proportion of 6%. Historically, we believe the systematic review supports an untreated rate of at least 15%. We have set the non-inferiority margin at 3.5% (i.e. a pharmacological alone rate under the null hypothesis of not more than 9.5%). We think this is justifiable on the grounds that clinicians would not tolerate more than a 3.5% absolute deterioration in VTE event rate over combination therapy, and that it preserves  $(9-3.5)/(15-6)$  or  $5.5/9$  i.e. 61% of the established treatment effect over no intervention (greater than the 50% minimum usually required by regulatory authorities for non-inferiority studies). At 90% power and using a one-sided 2.5% level of significance (equivalent to a two-sided 5%) level we would need to randomise 1936 participants in a fixed sample approach. We prefer to adopt a group sequential approach, giving 4 equally spaced formal interim analyses for efficacy (at 25%, 50%, 75% and a final analysis at 100% of the information) and one formal interim analysis for futility at 50% information. This flexibility to stop early on either efficacy or futility only marginally increases the maximum sample size to 2012 (4% increase, using East 6.3, Cytel Corporation 2014), a flexibility which is useful given the quality, relevance and uncertainty of the evidence base informing the sample size assumptions. If we conservatively allow for 10% loss to follow up, we would need to randomise no more than 2236 in total.

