#### 7.1.2 REVISED SAMPLE SIZE (APPLICABLE AFTER JANUARY 2018)

Due to the observed low event rate it was decided to abandon the group sequential design. It was clear from the blinded (aggregate) data that the overall population, subdivided by risk of primary outcome into 4 subpopulations by VTE risk crossed with age. i.e. Subpopulation #1 <65 years,

moderate risk of VTE; subpopulation #2 <65 years, high risk of VTE; subpopulation #3 ≥ 65 years at moderate VTE risk; subpopulation #4 ≥ 65 years at high VTE risk. ( With around 250 randomised overall in subpopulation 1 (<65, moderate VTE risk) with zero expected events (0 events observed in the first 180 randomised to Dec 2017), very few events in subpopulation 2 (<65, high VTE risk; around 750 randomised to Dec 2017, observed event 3/510 or 0.6% in the first 510 randomised); virtually no-one randomised into subpopulation 3 (≥65, moderate VTE risk); only 12 randomised to Dec 2017 (this subpopulation will be reported descriptively with no further consideration of formal sample size or inference), and for subpopulation 4 (≥65, and high VTE risk) 750 in subpopulation 4 (306 randomised to Dec 2017 with 11 events observed), the study will not observe sufficient events in total or specifically in subpopulation 4 (the only subpopulation still open to recruitment) to make a re-application of the sequential design sensible.

We have considered (as at Dec 2017) the implications for the sample sizes for the 4 subpopulations, and the Table below gives the detectable non-inferiority margins for indicative sample sizes (at 90% power and a 1-sided level of significance of 2.5%):

Subpopulation	Subpopulation #	Expected number randomised	Assumed event rate	Detectable non-inferiority margin
<65, Moderate	1	258	0.1%	1.30%
<65, High	2	733	0.6%	1.85%
≥65, Moderate	3	12	N/A	N/A
≥65, High	4	912	3.6%	4.0%

Note that these revised sample size calculations do not adjust for multiple comparisons; nor do they adjust for the original group sequential alpha spending (since no interim analyses took place). See Appendix 3- Rationale for Statistical Changes to the Protocol for further details.

The funder agreed to the revised sample size of 912 in subpopulation 4 in April 2018. The other 3 subpopulations (1-3) were closed to any further recruitment at this time, and we will analyse all available data in these 3 subpopulations.

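### The for-the-record analysis of cohorts 1-3 falls back on an original plan whose only stated margin, 3.5 points, was justified at a 6% VTE rate; the blinded rate in cohorts 1 and 2 is 0.43%, so no non-inferiority conclusion should be drawn from it

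*Protocol*

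**What the plan says.** Protocol section 7.2.1 describes the original analysis as a non-inferiority design. The primary outcome, VTE at 90 days, is to be analysed by mixed effects logistic regression with centre as a random effect. At the end of the same paragraph it adds: "We will undertake for the record the analysis of cohorts 1, 2 and 3 on those recruited prior to 20th December 2017 in line with" version 1.0 (the original) of the plan. It then says that under the new analysis the four cohorts are analysed separately, so participants in cohorts 1-3 appear in both.

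The original design is in section 7.1.1. It was powered "assuming an event rate of 6% of VTE at 90 days in the combined group and a non-inferiority margin of 3.5" percentage points, that is, "a pharmacological alone rate under the null hypothesis of not more than 9.5" percent. Two reasons are given for the margin: clinicians would not accept a larger absolute deterioration, and it preserves 61% of the effect over no intervention, taking 15% as the untreated rate and 6% as the treated rate. No other margin is given for the original plan.

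Section 7.1.2 reports the blinded data behind the redesign. Cohort 1 (under 65, moderate risk) had no events in the first 180 randomised. For cohort 2 (under 65, high risk) it gives "observed event 3/510 or 0.6% in the first 510 randomised". Cohort 3 (65 or over, moderate risk) had 12 participants and is to be reported descriptively, without formal inference.

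**The concern.** A non-inferiority margin on the absolute scale carries its meaning from the event rate it was set against. At 6%, 3.5 points allows a little over half as many events again. At a rate more than ten times lower, the same 3.5 points allows a large multiple of the control rate, and the 61% preservation argument no longer describes these patients. Section 7.2.1 sends cohorts 1-3 back to the plan that contains this margin and does not say whether a conclusion will follow.

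The risk is a statement that LMWH alone is non-inferior in younger and moderate-risk patients, produced mainly by the scarcity of events. Such a statement could be read as support for omitting stockings in a group where the blinded data showed three events. There is also an inconsistency: 7.1.2 excludes cohort 3 from inference, while 7.2.1 puts it back under an inferential plan.

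**Working it through.** **1. Reproduce the original design.** Inputs from 7.1.1: one-sided alpha 2.5%, power 90%, 6% in both arms, margin 0.035. Per arm, n = (1.960 + 1.282)² × 2 × 0.06 × 0.94 / 0.035² = 967.5, rounded up to 968, or 1936 in total. This matches the protocol's fixed-sample figure. Allowing 10% loss on the group sequential maximum, 2012 / 0.9 = 2235.6, rounded up to 2236, which also matches. So the margin acts as an absolute risk difference in the sample size calculation.

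**2. Rate in the retained cohorts.** Cohorts 1 and 2 together: (0 + 3) / (180 + 510) = 3/690 = 0.43%, exact 95% interval 0.09% to 1.27%. This is a blinded rate over both arms, used below as the stocking-arm rate. The event count in cohort 3 is not given.

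**3. What 3.5 points means at each rate.**
- Design: 9.5 / 6 = 1.58-fold.
- Cohorts 1 and 2: (0.43 + 3.5) / 0.43 = 3.93 / 0.43, about nine-fold.

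**4. Chance of meeting the margin.** Assumptions: cohorts pooled at the expected numbers in the 7.1.2 table (258 + 733 + 12 = 1003), 1:1 allocation, about 501 evaluable per arm. The margin is met when the upper limit of the two-sided 95% Newcombe interval for LMWH alone minus combined is below 3.5 points. That limit is (p2 − p1) + √[(u2 − p2)² + (p1 − l1)²], where p1 and p2 are the observed proportions on combined and on LMWH alone, and l1 and u2 are the Wilson lower and upper limits. Binomial probabilities are summed over all outcomes that pass, with p1 = 3/690.

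| True VTE rate on LMWH alone | Chance of meeting 3.5 points |
|---|---|
| 2 times | 99.5% |
| 3 times | 94% |
| 4 times | 78% |
| 5 times | 53% |
| 6 times | 30% |
| 8 times | 6% |

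With 2 events in the stocking arm, 10 on LMWH alone would still pass. Wald limits are more permissive (98% at three-fold). With 10% loss (451 per arm) the figures are about 91% at three-fold and just under half at five-fold.

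**5. Cohorts taken singly.** Cohort 2 (366 per arm, 0.6%): 89% at two-fold, 62% at three-fold, 33% at four-fold, 5% at six-fold. Cohort 1 (129 per arm): no events in either arm gives an upper limit of 2.9 points and passes; a single LMWH-alone event against none gives 4.3 points and fails.

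**6. The logistic model.** At the 7.1.2 rates, the expected total in cohorts 1 and 2 is 258 × 0.001 + 733 × 0.006 = 4.7 events, with three seen so far and none in cohort 1. A mixed model with a centre effect and covariates cannot be estimated reliably on that, and with no events in cohort 1 no odds ratio exists there. If 6% against 9.5% were converted to an odds-ratio margin (an assumption), it would be (0.095/0.905) / (0.06/0.94) = 1.64. With about 2.2 events per arm the standard error of the log odds ratio is about √(2/2.2 + 2/499) = 0.96, and the power at equal rates is Φ(ln 1.64 / 0.96 − 1.96), about 7%.

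**The case against.** The strongest reply is that 7.2.1 does not commit the trial to what the table tests. It says only that the analysis is for the record. It does not say that the cohorts are pooled, that the 3.5-point margin is applied as a risk difference, or that non-inferiority will be declared, and SAP v1.0 is not shown. The model named is logistic, and on an odds-ratio scale non-inferiority would almost never be shown. Section 7.2.2 places the final analysis and reporting under SAP V2.0, by subpopulation. All of this stands, so the probabilities are conditional. It does not remove the problem: on either scale the result is governed by the shortage of events, and labelling an analysis as a record does not say that no conclusion will be drawn from it.

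A reader might infer that non-inferiority would be declared whatever LMWH alone does. The figures do not support that. The pooled chance falls to 30% at six-fold and 6% at eight-fold, and when the true difference is exactly 3.5 points the rule passes 2.1% of the time, within the nominal 2.5%. The rule does discriminate on the absolute scale. Nor would the data be empty: 2 against 2 events in 501 per arm gives an upper limit of 1.1 points.

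A reader might also infer from the 1.30 and 1.85 point figures in 7.1.2 that cohorts 1 and 2 face two competing decision rules. Those figures are labelled detectable margins at 90% power for indicative sample sizes; the protocol does not make them pass-or-fail thresholds.

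Finally, 7.1.1 gives a clinical reason for 3.5 points as well as the preservation argument. That reason is stated as a deterioration from combination therapy assumed to run at 6%; the protocol does not argue that the same increase would be acceptable at 0.43%.

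**Conclusion.** The concern holds in a limited form. Section 7.2.1 keeps cohorts 1-3 under an original non-inferiority plan whose only stated margin has lost its effect-preservation justification at the observed rate: it tolerates about a nine-fold VTE rate where the design tolerated 1.58-fold. If applied as a risk difference to the pooled cohorts, it would very probably be met even if LMWH alone doubled or tripled VTE, and about half the time at five-fold. These figures assume pooling, 1:1 allocation, full evaluability, Newcombe limits and the blinded 0.43% as the stocking-arm rate; the lower chances for cohort 2 alone show how far they depend on pooling. Independently of those assumptions, the named logistic model is unsuited to about three to five events, and 7.2.1 is at odds with 7.1.2 on cohort 3. The protocol does not show that a non-inferiority declaration is planned; the defect is that it leaves one open.

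**What to change.** In 7.2.1, state that the for-the-record analysis of cohorts 1-3 (recruited before 20 December 2017) will report event counts by arm and the risk difference with an exact or score 95% confidence interval, and that no non-inferiority conclusion at the 3.5-point margin will be drawn from it. In the same edit, reconcile cohort 3 with 7.1.2, so that both sections treat it as descriptive. Carry the wording into the current SAP.

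The change is about one sentence in each document and needs no new data or participants. The trial gives up a formal non-inferiority verdict under the original plan for these cohorts; the interval still shows what absolute differences the data can exclude.

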### **7.2.2 REVISED DATA ANALYSIS (APPLICABLE AFTER JAN 2018)**

A single final analysis and reporting of the trial will occur in line with V2.0 of the Statistical Analysis Plan which was revised from version 1.0 (March 2016) in December 2018.

Under the revised analysis, subpopulations 1-4 as described in Appendix 3 will be analysed separately. Due to simplification it is no longer necessary to consider a group sequential design.

## 7.3 SUBGROUP ANALYSES

### 7.3.1 PLANNED SUBGROUP ANALYSES

There will be a subgroup analysis of moderate versus high baseline VTE risk, using a formal treatment VTE risk interaction term in the proposed model above for the primary outcome.

### 7.3.2 REVISED SUBGROUP ANALYSES

The original planned subgroup analyses have been abandoned as they are redundant given the change to statistical analysis of subpopulations 1-4.

## 7.4 PROPOSED FREQUENCY OF ANALYSES

There will be a single analysis at the final sample size for analysis and reporting of the main results. Confidential analyses will be presented to the iDMC at the agreed milestones under the group sequential design.

## 7.5 DATA MONITORING

### 7.5.1 ORIGINAL PLANNED DATA MONITORING

A group sequential design is proposed. The independent Data Monitoring Committee (iDMC) will formally examine data at 25%, 50%, 75% and at a final look at 100% of the information for effectiveness using a Lan-DeMets alpha spending function ( $<0.001$ , 0.002, 0.010, and 0.025 cumulative alpha spent) and at 50% for futility (0.02 of the 0.10 total cumulative beta spent). The trial at full size expects to observe around 156 VTE episodes at 90 days under the null hypothesis (that the single intervention is not non-inferior to the combined) and around 121 events under the alternative hypothesis (that the single intervention is non-inferior to the combined) so that in information time the interim looks will be scheduled to around 40 (25%), 80 (50%, including the single futility look as well) and 120 (75%) events recorded. The full details of the iDMC's remit (including the stopping rules for effectiveness and futility) will be agreed at the first meeting of the iDMC before any unblinded data are available or seen. The iDMC will meet to examine data at approximately 200 participants with outcome data at 90 days for the purpose of checking on the assumed underlying pooled event rate for the primary outcome at 90 days. The expected sample

size under the null hypothesis is 1546 and under the alternative hypothesis 1673 (having allowed for the 10% assumed to be missing primary outcome data).

Data and all appropriate documentation will be stored for a minimum of 10 years after the completion of the trial, including the follow-up period.

### **7.5.2 REVISED DATA MONITORING**

The iDMC will meet regularly in line with the iDMC Charter V2.0 without any formal interim analyses due to the abandonment of the group sequential analysis and the closure of recruitment to subpopulations 1-3. The rationale for abandonment is described in Appendix 3.

## **8. REGULATORY ISSUES**

### **8.1 ETHICS APPROVAL**

The trial will be conducted in accordance with the principles of good clinical practice (GCP).

The Chief Investigator (CI) has obtained approval from the Research Ethics Committee. The trial must be submitted for Site Specific Assessment (SSA) at each participating NHS Trust. The Chief Investigator will require a copy of the Trust R&D approval letter before accepting participants into the trial. The trial will be conducted in accordance with the recommendations for physicians involved in research on human subjects adopted by the 18th World Medical Assembly, Helsinki 1964 and later revisions.

### **8.2 CONSENT**

Consent to enter the trial must be sought from each participant only after a full explanation has been given, an information leaflet offered and time allowed for consideration. Signed participant consent should be obtained. The right of the participant to refuse to participate without giving reasons must be respected. After the participant has entered the trial the clinician remains free to give alternative treatment to that specified in the protocol at any stage if he/she feels it is in the participant's best interest, but the reasons for doing so should be recorded. In these cases the participants remain within the trial for the purposes of follow-up and data analysis. All participants are free to withdraw at any time from the protocol treatment without giving reasons and without prejudicing further treatment.

### **8.3 CONFIDENTIALITY AND DATA PROTECTION**

The CI and trial staff involved with this trial will comply with the requirements of the Data Protection Act 1998 with regard to the collection, storage, processing and disclosure of personal information and will uphold the Act's core principles. The CI and trial staff will also adhere, if appropriate, to the current version of the NHS Scotland Code of Practice on Protecting Participant Confidentiality. Access to collated participant data will be restricted to the CI and appropriate trial staff. Computers used to collate the data will have limited access measures via user names and passwords.

Published results will not contain any personal data that could allow identification of individual participants.

All evaluation forms, reports, and other records will be identified in a manner designed to maintain participant confidentiality. All records will be kept in a secure storage area with limited access to trial staff only. Clinical information will not be released without the written permission of the participant, except as necessary for monitoring and auditing by the Sponsor or its designee. The CI and trial staff involved with this trial will not disclose or use for any purpose other than performance of the trial, any data, record, or other unpublished, confidential information disclosed to those individuals for the purpose of the trial. Prior written agreement from the Sponsor or its designee will be obtained for the disclosure of any said confidential information to other parties.

#### **8.4 INDEMNITY**

Imperial College London holds negligent harm and non-negligent harm insurance policies which apply to this trial. Imperial College Healthcare NHS Trust holds standard NHS Hospital Indemnity and insurance cover with NHS Litigation Authority for NHS Trusts in England, which apply to this trial.

